If a subject experiences a clinically significant and/or unacceptable toxicity, dosing will be interrupted and supportive therapy administered as required.

5.1.1.1 Management for Treatment-Related Toxicity of TAS 102

5.1.1.1.1 Non-hematologic toxicities of TAS 102

Table 3. Non-hematologic toxicity management

Grade¶	Dose hold/resumption within a 28-day treatment cycle	Dose adjustment for next cycle
Grade 1 or 2		
Any occurrence	Maintain treatment at the same dose level	None
Grade 3* or higher		
1 st , 2 nd or 3 rd occurrence	Suspend treatment until Grade 0 or 1	Reduce by 1 dose level from the previous level
4 th occurrence	Discontinue treatment	Discontinue treatment

¶ At the discretion of the investigator, patients may continue on study medication at the same dose without reduction or interruption for AEs (irrespective of grade) considered unlikely to become serious or life-threatening (including, but not limited to, fatigue, alopecia, changes in libido, and dry skin).

* Except for grade 3 nausea and/or vomiting controlled by antiemetic therapy or diarrhea responsive to antidiarrheal medication. Moreover, if grade 4 non-hematotoxicity that is related to the protocol therapy is observed, protocol therapy is to be discontinued. However, in case of adverse events, which can clearly be judged to have derived from the primary disease, depending on the judgement of the investigator (subinvestigator) protocol therapy can be continued. In this case, the reason for this judgement must be recorded in the medical records, etc. (For example: Grade 3 cancer pain that is associated with the primary disease, Grade 3 weight loss that is associated with the primary disease, etc.)

5.1.1.1.2 Hematologic toxicities of TAS 102

Criteria for dose hold and resumption in response to hematologic toxicities related to myelosuppression are described in Table 2.

Uncomplicated neutropenia or thrombocytopenia \leq grade 3 does not require a reduction in dose of study medication. Patients who experience uncomplicated Grade 4 neutropenia or thrombocytopenia that results in a >1 week delay of the start of the next cycle should start the next cycle with dose reduction in $5\text{mg}/\text{m}^2$ step. If toxicity remains despite 4 dose reductions or at a minimum dose ($15\text{mg}/\text{m}^2$ twice a day), discontinue TAS 102.

Table 4. Hematologic toxicity management

Parameter	Hold Criteria		Resumption Criteria*	Dose adjustment for next cycle
	Conventional Units	SI units		

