Neutrophils	<500/mm ³	<0.5x10 ⁹ /L	≥1500/mm ³ (IU: ≥1.5x10 ⁹ /L)	Details below¶
Platelets	<50,000/mm ³	<50x10 ⁹ /L	≥75,000/mm ³ (IU: ≥75x10 ⁹ /L)	Details below¶

* These resumption criteria apply to the start of the next cycle for all patients regardless of whether or not the hold criteria were met. Both conventional and SI (International System) units are presented in CTCAE v. 5.

¶ 1) ≤ Grade 3 neutropenia or thrombocytopenia

- If there are no complications (such as fever, infection or hemorrhage), there is no need to reduce the dose of TAS 102
- If there are complications, the necessity of reducing dose should be considered also with regard to safety.
- For neutropenia, pegfilgrastim or filgrastim can be administered at investigator's discretion.

2) Grade 4 neutropenia or thrombocytopenia

- When there are no complications, but initiation of the next cycle is delayed by more than one week, dose should be reduced by 1 level (Table 1) when starting next cycle (dose is not reduced when administered on the same weekday). If initiation is not delayed by more than one week, the next cycle can be initiated at the same dose level.
- If there are complications, in consideration of the safety of the patient, dose should be reduced by 1 level (Table 1) when starting the next cycle.
- For neutropenia, pegfilgrastim or filgrastim can be administered at investigator's discretion.

5.1.1.1.3 Dose resumption timing of TAS 102

If the patient recovers from the toxicities to the resumption criteria defined above during the 2-week treatment period (treatment Days 1 through 5, 8 through 12), and no dose reduction is required, study drug therapy may be resumed during that cycle.

If a dose reduction is required, study drug therapy should be resumed at the start of the next cycle at the appropriate dose level according to instructions provided in Table 1 and 2. If the study drug dose is reduced, it must not be increased for subsequent cycles.

If the toxicities that are defined above recover during the recovery period (Days 13 through 28), start the next cycle on schedule at the appropriate dose level according to instructions provided in Table 1, 3 and 4.

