5.2 Concomitant therapy

- All patients should be maintained on the same medications throughout the study period, as medically feasible;
- The investigator should instruct the patient to notify the study staff about any new medications he/she takes after the start of the study drug. All medications (other than study drug) and significant non-drug therapies (including physical therapy and blood transfusions) administered after the patient starts treatment with study drug must be recorded;
- Administration of pegfilgrastim or filgrastim following initiation of protocol therapy is at investigator's discretion for all patients;
- Administration of erythropoietin or darbopoietin is allowed;
- Administration of bisphosphonates is permitted at the investigator's discretion
- Transfusions of red blood cells, platelets, or other blood products are permitted at the investigator's discretion
- Patients must be instructed not to take any additional medications (including herbal supplements and over-the-counter products) during the trial without prior consultation with the investigator. All medications taken within 30 days of screening should be recorded. If concomitant therapy must be added or changed, the reason and name of the drug/therapy should be recorded;
- In general, the use of any concomitant medication/therapies deemed necessary for the care of the patient are allowed, including drugs given prophylactically (e.g. antiemetics or steroids).
- Premedication is recommended before ramucirumab administration (including first dose). Recommended premedication agents include histamine H1 antagonists such as diphenhydramine hydrochloride 50 mg I.V. (or equivalent). Additional premedication may be provided at the investigator's discretion.

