8.1 Adverse Events

8.1.1 Definitions

A serious adverse event is an undesirable sign, symptom or medical condition which:

1. Is fatal or life-threatening.
2. Requires or prolongs hospitalization.
3. Results in persistent or significant disability/incapacity.
4. Constitutes a congenital anomaly or a birth defect.
5. Is medically significant, may jeopardize the subject and may require medical or surgical

intervention to prevent one of the outcomes listed above.

Information about all adverse events, whether volunteered by the subject, discovered by investigator questioning, or detected through physical examination, laboratory test or other means, will be collected and recorded and followed as appropriate. An adverse event is any undesirable sign, symptom or medical condition occurring after starting study treatment.

Medical conditions/diseases present before starting study treatment are only considered adverse events if they worsen after starting study treatment. Abnormal laboratory values or test results constitute adverse events only if they induce clinical signs or symptoms or require therapy.

Full information from serious adverse events as well as adverse events concerning medication errors and overdose will be reported to Taiho Drug Safety or Designee. **This can be performed by faxing it to Taiho or designee at [contact] or via e-mail at [contact] (please note the underscore between '102' and 'Safety').**

In addition to the above, fatal events will also be documented by a separate death form, instead of reporting them as AE CTCAE grade.

Events not considered to be serious adverse events are hospitalizations for the:

- Routine treatment or monitoring of the studied indication, not associated with any deterioration in condition.
- Treatment, which was elective or pre-planned, for a pre-existing condition that did not worsen.
- Treatment on an emergency, outpatient basis for an event not fulfilling any of the definitions of serious given above and not resulting in hospital admission.

Pregnancy, although not itself a serious adverse event, should also be reported on a serious adverse event form or pregnancy form and be followed up to determine outcome, including spontaneous or voluntary termination, details of birth, and the presence or absence of any birth defects or congenital abnormalities.

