9.3 Statistical analysis

Overall survival (OS) is defined as the time from starting on trial to date of death due to any cause and progression-free survival (PFS) is defined as the duration of time from start of treatment to time of progression or death, whichever comes first. The final analysis will be conducted after the follow-time of the last patient exceeds 6 months. The primary endpoint of the study is OS at 6 month. The experimental treatment will be deemed to have good activity if ≥ 15 out of 25 evaluable patients survive 6 months or more. OS will be estimated using the Kaplan-Meier method and the two-sided 95% confidence interval (CI) for median OS will be computed using log-log transformation.

The secondary endpoints in this study include toxicity, PFS and the objective response rate (ORR) defined as (complete response (CR) + partial response (PR)) using RECIST 1.1 criteria (Appendix A). ORR will be reported with 95% CI computed by the Clopper-Pearson method. The frequency and severity of adverse events and tolerability of the regimen will be summarized using descriptive statistics. PFS with 95% CI will be estimated. As exploratory objective, the association between biomarkers and clinical outcomes (ORR, OS and PFS) will be examined using multiple logistic regression and the multivariable Cox regression model. A p-value of <0.05 will be considered statistically significant. Frequency and severity of adverse events will be summarized using descriptive statistics.

10. Data Recording

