APPENDIX A: RECIST Criteria for Measuring Tumor Response Antitumor Effect

Response and progression will be evaluated in this study using the new international criteria proposed by the revised Response Evaluation Criteria in Solid Tumors (RECIST) guideline (version 1.1) (Eisenhauer et al., 2009). Changes in the largest diameter (unidimensional measurement) of the tumor lesions and the shortest diameter in the case of malignant lymph nodes are used in the RECIST criteria.

Definitions

Evaluable for toxicity. All patients will be evaluable for toxicity from the time of their first treatment with ramucirumab or TAS 102.

Evaluable for objective response. Only those patients who have measurable disease present at baseline, have received at least one cycle of therapy, and have had their disease re-evaluated

will be considered evaluable for response. These patients will have their response classified according to the definitions stated below. (Note: Patients who exhibit objective disease progression prior to the end of cycle 1 will also be considered evaluable.)

Disease Parameters

Measurable disease. Measurable lesions are defined as those that can be accurately measured in at least one dimension (longest diameter to be recorded) as ≥ 10 mm with CT scan, MRI or calipers by clinical exam. All tumor measurements must be recorded in millimeters (or decimal fractions of centimeters).

Note: Tumor lesions that are situated in a previously irradiated area might be considered measurable if the lesion has increased in size since the radiation.

Malignant lymph nodes. To be considered pathologically enlarged and measurable, a lymph node must be ≥ 15 mm in short axis when assessed by CT scan (CT scan slice thickness recommended to be no greater than 5 mm). At baseline and in follow-up, only the short axis will be measured and followed.

Non-measurable disease. All other lesions (or sites of disease), including small lesions (longest diameter < 10 mm or pathological lymph nodes with ≥ 10 to < 15 mm short axis), are considered non-measurable disease. Bone lesions, leptomeningeal disease, ascites, pleural/pericardial effusions, lymphangitis cutis/pulmonitis, and abdominal masses (not followed by CT or MRI), are considered as non-measurable.

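### The toxicity summary in 9.3 can omit asymptomatic, untreated grade 3–4 cytopenias, because 8.1.1 does not count them as adverse events

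*Combined protocol and SAP*

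**What the plan says.** Section 8.1.1 defines adverse events (AEs) and then limits the definition for laboratory findings: "Abnormal laboratory values or test results constitute adverse events only if they induce clinical signs or symptoms or require therapy". What counts as requiring therapy is not defined.

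Section 9.3 states: "The secondary endpoints in this study include toxicity, PFS and the objective response rate". For the safety part it specifies one analysis: "The frequency and severity of adverse events and tolerability of the regimen will be summarized using descriptive statistics". Neither 9.1 nor 9.3 defines tolerability, and no laboratory table is named. Appendix A sets the population: "All patients will be evaluable for toxicity from the time of their first treatment with ramucirumab or TAS 102".

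The treatment sections expect severe counts without symptoms. Section 5.1.1.1.2 has a rule that begins "Patients who experience uncomplicated Grade 4 neutropenia or thrombocytopenia that results in a" delay of more than one week to the next cycle. Supportive treatment is discretionary: "For neutropenia, pegfilgrastim or filgrastim can be administered at" the investigator's discretion (Table 4 notes), and "Transfusions of red blood cells, platelets, or other blood products are permitted at the" investigator's discretion (5.2).

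On deaths, 8.1.1 says: "fatal events will also be documented by a separate death form, instead of reporting them as AE CTCAE grade".

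**The concern.** Secondary objective 1 is the frequency and severity of AEs, and the tolerability, of a combination for which Section 3 itself warns of unexpected toxicity. The protocol grades laboratory toxicity by CTCAE v5 and acts on it without asking for symptoms, but the analysis is tied to a record that asks for symptoms or therapy. Three consequences follow.

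- The reported toxicity can be lower than the toxicity observed.
- Two patients with the same neutrophil count can be reported differently because one received a growth factor and the other did not.
- An event that counted as a dose-limiting toxicity (DLT) can be absent from the safety summary.

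**Working it through.** The plan gives no figure for this point, so the check is a comparison of sections followed by a range.

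**Step 1. Sections side by side**

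| Event | How the plan handles it | AE under 8.1.1? |
|---|---|---|
| Asymptomatic, untreated grade 3 neutropenia or thrombocytopenia | Graded by CTCAE v5 (5.1.1); no TAS 102 reduction needed if uncomplicated (Table 4) | No |
| Asymptomatic, untreated grade 4 count, next cycle not delayed by more than a week | Same dose level allowed (Table 4) | No |
| Same, next cycle delayed by more than a week | TAS 102 reduced one level (Table 4); 5.1.1 describes TAS 102 reductions as being for AEs | Sections conflict |
| Grade 4 neutropenia for 7 days or more, or grade 4 thrombocytopenia, in the DLT window | DLT on the count alone (Sections 3 and 5.1) | No, if asymptomatic and untreated |
| Urine protein 2–3 g/24 hours | Ramucirumab held, then resumed at a lower level, on the urine result alone (5.1.1.2.4); 5.1.1 and 5.1.1.2 class proteinuria with the ramucirumab AEs | Sections conflict |
| Febrile neutropenia | DLT at grade 3 or higher | Yes; fever is a clinical sign |

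Serious-event reporting does not bring the missing rows back by default. Section 8.3 leaves out an isolated grade 4 laboratory value unless the investigator judges that it meets the ICH criteria for a serious event.

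**Step 2. Range for neutropenia**

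Inputs: 25 evaluable patients, 15 of them in stage 1 (9.2); grade 3 or higher neutropenia 34% and febrile neutropenia 2%, from a phase III study of TAS 102 without ramucirumab (1.4). The 2% is read as a share of all patients. Let q be the share of non-febrile cases that are symptomatic or treated. The documents do not give q.

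- Grade 3 or higher: 25 × 0.34 = 8.5 patients
- Febrile: 25 × 0.02 = 0.5
- Non-febrile: 8.5 − 0.5 = 8.0
- Omitted from the AE summary: 8.0 × (1 − q)
- Rate shown in the AE summary: 2% + 32% × q

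| q (assumed) | Patients omitted, of 25 | Rate shown |
|---|---|---|
| 0 | 8.0 | 2% |
| 0.5 | 4.0 | 18% |
| 1 | 0 | 34% |

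For the 15 stage 1 patients the upper end is 15 × 0.32 = 4.8. If 2% instead means 2% of neutropenia cases, the upper end for 25 patients is 25 × 0.34 × 0.98 = 8.3.

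The documents give no rate for grade 4 neutropenia of 7 days or more, grade 4 thrombocytopenia, or urine protein of 2–3 g/24 hours. Those omissions cannot be sized.

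**The case against.** The strongest reply is that the rest of the protocol treats these findings as AEs. Section 5.1.1 introduces TAS 102 reductions as a response to AEs. Sections 5.1.1 and 5.1.1.2 allow ramucirumab reduction only for proteinuria and then refer to the remaining ramucirumab events as other AEs. Section 1.4 lists cytopenias among the most common AEs, and 8.1.1 says AEs may be found by laboratory test. This stands in part. A reader might infer that 8.1.1 plainly excludes dose-modifying proteinuria and cytopenias from the AE record. The documents do not support that; for those events the sections conflict. The reply does not reach asymptomatic, untreated counts that lead to no dose reduction. There the explicit condition in 8.1.1 is the only specific rule, and being detectable by a laboratory test does not remove it.

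Second, tolerability could naturally cover DLTs, holds and reductions, and 8.2 assesses safety and tolerability by CTCAE v5. That is a reasonable expectation, but nothing in 9.3 commits to it.

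Third, the laboratory data are collected and monitored anyway (7.3, 8.2). That is correct: the gap is in analysis and reporting, not in data capture, which is why the remedy is cheap.

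Fourth, 0 to 8 is the full logical range for an unknown q, taken from a different regimen and with grades 3 and 4 pooled. That also stands; the range bounds the effect and does not estimate it.

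Finally, a reader might infer from the death-form sentence that deaths go unrecorded. They do not. A fatal event is the first criterion for a serious event in 8.1.1, and death is the event in overall survival. Because the sentence also presents the form as an addition, the only uncertainty is whether fatal AEs appear as grade 5 in the severity summary.

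**Conclusion.** The point holds for asymptomatic, untreated grade 3–4 neutropenia and thrombocytopenia, including a DLT defined by the count alone. Applied as written, 8.1.1 and 9.3 can leave these out of the toxicity endpoint, and inclusion can turn on discretionary supportive care. For proteinuria and cytopenias that lead to dose modification, the finding is narrower: the sections disagree and must be reconciled.

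For neutropenia, 0 to about 8 of 25 patients could be omitted. This assumes the quoted TAS 102 rates carry over to the combination and leaves the symptomatic-or-treated share open from 0 to 1. It should not be read as a forecast that 8 patients will be missed.

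Nor does it follow that the trial's decisions are compromised. DLT decisions and dose holds rest on their own criteria, and the primary endpoint is survival at 6 months; none depends on the 8.1.1 definition. The grade 5 question is a minor labelling ambiguity.

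**What to change.** The AE definition need not change. In 9.3, for all patients evaluable for toxicity under Appendix A:

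- Add a treatment-emergent laboratory table from all collected hematology and chemistry, scheduled and unscheduled. Show worst post-baseline CTCAE v5 grade per patient against baseline grade, as a shift table. The baseline column matters because 4.1 admits abnormal values (hemoglobin just above 8.0 g/dl; AST, ALT or alkaline phosphatase up to 5 × ULN with liver involvement), and 8.1.1 counts pre-existing conditions only if they worsen.
- Add the highest 24-hour urine protein per patient in the bands of 5.1.1.2.4 (below 2, 2–3, above 3 g). Include one category for not collected because the dipstick was below 2+ and another for required but missing, since the collection is made only after a dipstick of 2+ or more.
- Label the table as a minimum. Scheduled draws fall on Days 1 and 15 of a 28-day cycle, about 14 days apart, so values between draws are not seen.
- List every DLT and every laboratory-driven dose hold or reduction, whether or not it was recorded as an AE.

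Reconcile 8.1.1 with 5.1.1 and 5.1.1.2 on whether laboratory findings that lead to dose modification are AEs. As a minor clarification, state that fatal AEs are tabulated as grade 5 in addition to the death form.

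The cost is one more table, a listing and a few sentences. No new test is needed: hematology and chemistry are already scheduled, and 24-hour urine is already collected when indicated. The downside is that the reported toxicity rate may be higher.

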1. To determine the frequency and severity of adverse events and tolerability of TAS 102 plus ramucirumab in patients with advanced, refractory gastric and GEJ adenocarcinoma
2. To determine the efficacy of TAS 102 in combination with ramucirumab based on Response Evaluation Criteria in Solid Tumors (RECIST) v1.1
3. To determine the progression free survival in patients with advanced, refractory gastric and GEJ adenocarcinoma receiving TAS 102 in combination with ramucirumab.

Exploratory Objective

1. To explore potential correlation between blood biomarkers and clinical outcome using a multiplex assay evaluating circulating angiogenic biomarkers (see 12.1 Correlative study)

3. Study Design

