5.1.1 Management (dose Modifications and dose delays) for Treatment-Related Toxicity

All toxicities will be graded according to National Cancer Institute's (NCI's) Common Terminology Criteria for Adverse Events (CTCAE) (NCI CTCAE v 5). The study investigator will determine if either or both medications should be held.

Dose reductions for AEs related to TAS 102 are permitted dose reductions to a minimum dose of 20mg/m² twice a day in 5mg/m² steps. After dose reduction, escalation of dose is not allowed.

Table 1. TAS 102 dose modifications

TAS 102 dose (BID)	BSA (m ²)*	Dosage in mg (BID)	Total daily dose (mg)	Tablets per dose	
				15mg	20mg
Starting dose					
35mg/m ²	<1.07	35	70	1	1
	1.07-1.22	40	80	0	2
	1.23-1.37	45	90	3	0
	1.38-1.52	50	100	2	1
	1.53-1.68	55	110	1	2
	1.69-1.83	60	120	0	3
	1.84-1.98	65	130	3	1
	1.99-2.14	70	140	2	2
	2.15-2.29	75	150	1	3
	≥ 2.30	80	160	0	4
Level 1 dose reduction: from 35mg/m ² to 30mg/m ²					
30mg/m ²	<1.09	30	60	2	0
	1.09-1.24	35	70	1	1
	1.25-1.39	40	80	0	2
	1.4-1.54	45	90	3	0
	1.55-1.69	50	100	2	1

	1.70-1.94	55	110	1	2
	1.95-2.09	60	120	0	3
	2.10-2.28	65	130	3	1
	≥ 2.29	70	140	2	2
Level 2 dose reduction: from 30mg/m ² to 25mg/m ²					
25mg/m ²	<1.10	25	50	2 (PM)¶	1 (AM)¶
	1.10-1.29	30	60	2	0
	1.30-1.49	35	70	1	1
	1.50-1.69	40	80	0	2
	1.70-1.89	45	90	3	0
	1.90-2.09	50	100	2	1
	2.09-2.29	55	110	1	2
	≥ 2.30	60	120	0	3
Level 3 dose reduction: from 25mg/m ² to 20mg/m ²					
20mg/m ²	<1.14	20	40	0	1
	1.14-1.34	25	50	2 (PM)¶	1 (AM)¶
	1.35-1.59	30	60	2	0
	1.60-1.94	35	70	1	1
	1.95-2.09	40	80	0	2
	2.10-2.29	45	90	3	0
	≥ 2.29	50	100	2	1

* Calculate BSA to 2 decimal places.

¶ At a total daily dose of 50mg, patients should take 1 x 20mg tablet in the morning and 2 x 15mg tablets in the evening.

Dose reductions of ramucirumab will be allowed only for proteinuria with 6 mg/kg for first episode of proteinuria (> 2 g/24 hours) and with 5 mg/kg for second episode of proteinuria (> 2 g/24 hours). Only dose delay will be allowed for the other AEs related to ramucirumab.

Table 2. Ramucirumab dose modifications

Starting dose	8mg/kg
Level 1 dose reduction	6mg/kg
Level 2 dose reduction	5mg/kg

Dose modifications will not be required for AEs that are clearly not attributed to TAS 102 or ramucirumab (such as an accident) or for laboratory abnormalities that are not deemed to be clinically significant.

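### Section 8.1.1 takes fatal adverse events off the CTCAE scale, contradicting the sections that grade all toxicities, and Section 9.3 has no rule to bring them into the severity summary

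*Combined protocol and SAP*

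**What the plan says.** The rule on fatal events is one sentence in Section 8.1.1. After an opening phrase that adds it to the reporting described just before, it says that "fatal events will also be documented by a separate death form, instead of reporting them as AE CTCAE grade". The same section makes a fatal outcome part of the first criterion for a serious adverse event ("Is fatal or life-threatening") and says that progression of the cancer under study is not an adverse event.

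The grading rule appears in three other places. Section 5.1.1 states: "All toxicities will be graded according to National Cancer Institute's (NCI's) Common Terminology Criteria for Adverse Events (CTCAE) (NCI CTCAE v 5". Note b to the calendar in Section 6.8 applies CTCAE version 5 to all toxicities and adverse events, and Section 8.2 names the same scale for safety and tolerability. None of the three makes an exception for fatal events.

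The first secondary objective in Section 2 is "To determine the frequency and severity of adverse events and tolerability of TAS 102 plus ramucirumab". Section 9.3 lists toxicity among the secondary endpoints and gives this analysis: "The frequency and severity of adverse events and tolerability of the regimen will be summarized using descriptive statistics". It closes with a second sentence to the same effect: "Frequency and severity of adverse events will be summarized using descriptive statistics". Neither sentence mentions fatal events, the death form or attribution.

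**The concern.** Severity is half of the first secondary objective, and CTCAE grade is the protocol's only stated scale for assessing it. A site that follows 8.1.1 would report a fatal hemorrhage, perforation or neutropenic infection as a serious adverse event and complete a death form, but would assign no grade 5. In a table by grade, the event would then have no grade or would sit at the highest grade recorded before death. Either way the table would end at grade 4, and a reader could take that to mean that no treatment-related death occurred.

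The setting makes this more than a matter of form. Section 1.3 lists hemorrhage and gastrointestinal perforation among the ramucirumab warnings, and Section 3 says that unexpected toxicities can occur with the combination. Section 3 also bases an early safety decision on the number of dose limiting toxicities in the first 6 patients, and that definition is written in grades.

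**Working it through.** No figure in the documents bears on this point, so the check sets the texts side by side.

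1. **What the 8.1.1 sentence does.** Its opening phrase and the word 'also' add the death form to the reporting of serious adverse events. Its last clause then substitutes the form for the CTCAE grade. Read literally, reporting as a serious event stays and the grade goes.

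2. **Whether another section settles the conflict.** Sections 5.1.1, 6.8 and 8.2 grade without exception. Section 8.1.1 is the only text specific to fatal events, so a data manager could reasonably treat it as governing. No order of precedence is stated.

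3. **Whether the event is still captured.** Yes. Section 8.3 puts all adverse events on the CRF with dates of onset and resolution, seriousness, outcome and relationship to study drug. Grade is not in that list, so 8.3 keeps the event but does not restore its grade.

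4. **Whether the analysis brings it back.** Section 9.3 has no rule for this. Deaths enter OS, which counts death from any cause, and PFS. Neither separates a treatment-related death from one due to the cancer, so neither can stand in for a count of fatal toxicities.

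5. **Dose limiting toxicity.** Sections 3 and 5.1 define it by grade: for example, grade 3 or higher for most non-hematological toxicity and for febrile neutropenia. The text does not say how a fatal toxicity without a grade meets that definition.

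6. **Scale, for context only.** With 25 treated patients, one affected patient is 1/25 = 4 percentage points. This is an upper limit: Appendix A makes every patient evaluable for toxicity from first treatment, while Section 9.2 replaces patients inevaluable for the primary endpoint, so the safety denominator may exceed 25. The documents give no fatal-toxicity rate. Under an assumed rate q, the chance of at least one fatal toxicity among n patients is 1 − (1 − q)^n:

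| Assumed q | n = 6 | n = 25 |
|---|---|---|
| 1% | 1 − 0.99^6 = 6% | 1 − 0.99^25 = 22% |
| 2% | 1 − 0.98^6 = 11% | 1 − 0.98^25 = 40% |
| 5% | 1 − 0.95^6 = 26% | 1 − 0.95^25 = 72% |
| 10% | 1 − 0.90^6 = 47% | 1 − 0.90^25 = 93% |

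These are chances that the situation arises, not that an event is misreported. The range is too wide to do more than show that the case is worth providing for.

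**The case against.** The strongest reply is that the 8.1.1 sentence is poorly drafted rather than a real exclusion. It says both 'also' and 'instead', and three other sections would lead a site to enter grade 5. A fatal event is still a serious adverse event, is reported to the manufacturer's drug safety unit within 24 hours with a narrative and careful attention to causality (8.3), and is on the CRF with its outcome and relationship. An analyst could rebuild the grade 5 count from those fields. Under Section 8.2 the Protocol Monitoring Committee also meets monthly and reviews patterns and frequencies of all adverse events. The CRF and death form are not among the documents, so how they show a fatal outcome cannot be checked.

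Most of this stands, and it rules out the stronger readings. A reader might infer that the severity table can never show a grade 5 event, or that all fatal events are lost. Neither follows, because the other sections point the other way and the events are captured. A reader might also infer that the plan forfeits a comparison with the phase III TAS 102 trial that Section 1.4 describes in grade 5 terms. That is one background sentence about neutropenia, and no safety comparison is planned. Nor do the documents say that this is the first trial of the combination.

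The reply does not remove the contradiction. That a count could be rebuilt does not help if nothing tells the analyst to rebuild it.

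**Conclusion.** The point holds as a contradiction plus a missing analysis rule. Section 8.1.1 conflicts with 5.1.1, 6.8 and 8.2 over whether a fatal adverse event receives a CTCAE grade, and 9.3 does not say how such an event enters the toxicity summary. The consequence is conditional: if 8.1.1 is followed, the summary shows no grade 5 events and the status of a fatal toxicity under the grade-based definition of dose limiting toxicity is unclear. If the other sections are followed, grade 5 appears as usual.

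The effect is misclassification of severity, at most 4 percentage points per affected patient with 25 or more patients in the safety denominator. The primary endpoint and the two-stage design are untouched. The correction should be made because it concerns a declared secondary endpoint and costs very little.

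**What to change.** - **Section 8.1.1.** Replace the last clause of the sentence: an adverse event with fatal outcome is recorded on the adverse event CRF as CTCAE grade 5 with its attribution, and the death form is completed in addition. Deaths due only to progression of the cancer, which the section does not count as an adverse event, go on the death form alone.
- **Section 9.3.** State that fatal adverse events are included in the severity table and listed by attribution, and keep one of the two duplicate sentences on the descriptive summary.
- **Sections 3 and 5.1.** Reconcile the definition of dose limiting toxicity with the revised 8.1.1, so that the standing of a fatal toxicity is explicit. The content of that definition is for the clinical team.

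The cost is a sentence or two in 8.1.1, one in 9.3, a cross-check of the dose limiting toxicity text and one line in the adverse event table. The CRF entry, the serious event report and the death form are already planned, so no new data collection is needed.
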